12.4 Calculation or derivation of pharmacodynamic variable(s)

12.4.1 Plasma glucose level 20 minutes post release of the hypoglycaemic clamp

The primary efficacy of the study is the plasma glucose level 20 minutes post release of the hypoglycaemic clamp, where a statistically significant difference is anticipated between glucagon treatment and spontaneous recovery from hypoglycaemia.

12.4.2 Time to recovery from hypoglycaemia

The secondary outcome variables of the study are defined as the time (in minutes) from release of the hypoglycaemic clamp, after 30 minutes at plasma glucose 2.7 mmol/L, to the time point where two consecutive plasma glucose levels ≥ 3.5 mmol/L and ≥ 5.0 mmol/L respectively, have been measured.

12.5 Calculation or derivation of the relationship between pharmacokinetic and pharmacodynamic variables (Not applicable)

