4.1 Overall study design and flow chart

In total, 10 T2DM patients treated with Metformin, aged ≥ 18 to ≤ 75 years, will participate in the study to ensure 8 evaluable patients, hereafter called subjects.

The total study period is approximately 4-8 weeks and includes four visits to the clinic, see [Figure 1](#).

Visit 3, treatment/residential period

Each subject will enter a titration phase of two days, with 7-point plasma glucose monitoring, starting at 40 mg bid for one day and increased to 80 mg bid, if tolerated, the second day. Thereafter the tolerated dose, 40 or 80 mg bid, will be maintained for two more days.

The subjects will then (Day 5) be randomised to one of two treatment arms in a cross-over manner, where the full daily oral dose of AZD1656 will be given in the morning under fasting condition to induce hypoglycaemia. The treatment sequence will be given in the randomisation list. The single dose will be followed by either a subsequent injection of glucagon or spontaneous recovery from hypoglycaemia by the CR response depending on treatment arm.

After a recovery phase of two days (Day 6 and 7) where AZD1656 will be maintained at the same dose bid as Day 3-4, subjects will be subjected to a new period of controlled hypoglycaemia followed by alternate treatment as to the previous hypoglycaemic study period, see [Figure 1](#).

On Day 5 and 8, after an overnight fast, the full daily dose from Day 3-4 (80 mg or 160 mg) will be given as a single oral dose (time 0 min). Blood samples for glucose and hormone analyses will be drawn from a catheter in a cubital vein. Another vein will be used for infusion of insulin and/or glucose, controlled by the Biostator[®], in order to reach glycaemic plateaus of 5 mmol/L (0 to 60 min), 4 mmol/L (60 to 90 min), and 3.2 mmol/L (90 to 150 min). Plasma glucose will then be clamped to a target nadir of 2.7 mmol/L and released at 180 min, ie, insulin infusion will be stopped, see [Figure 3](#).

The fasting state will be maintained 270 min after dosing. Plasma glucose will be followed continuously. When plasma glucose has been clamped aiming at 2.7 mmol/L for 30 minutes (ie, 180 min after dose), the clamp will be released and either 1 mg glucagon will be

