administered intra muscular or a spontaneous recovery in glucose levels will be awaited. After the release of the hypoglycaemic clamp, the Biostator[®] will continue to follow glucose on a minute by minute basis at least until two consecutive plasma glucose values are obtained at or above 5.0 mmol/L without concomitant glucose infusion. The Biostator's glucose analyzer will be re-calibrated in regular intervals by means of a YSI STAT2300 glucose analyzer throughout the clamp procedure, at least every 10-15 minutes.

Ninety minutes past clamp release (4.5 h post dose), the subjects will be served a meal with food ad libitum. Plasma glucose, counter regulatory hormones and pharmacodynamic (PD) markers will be followed for 3 hours after the clamp release (6 h post dose).

In order to avoid prolonged hypoglycaemia, a reversed clamp will be applied at 240 minutes post dosing with AZD1656. A glucose infusion will be used as needed to achieve a minimum plasma glucose level of 3.2 mmol/L at 240-270 min, 4.0 mmol/L at 270-300 min and ≥ 5.0 mmol/L after 300 min post dosing with AZD1656. The Biostator[®] will be disconnected at 360 min post dosing with AZD1656 provided that two consecutive plasma glucose values of at least 5.0 mmol/L are measured without ongoing glucose infusion. Plasma glucose values will be monitored also during the recovery period, Day 6-7, and in the morning on the day of discharge (Day 9), see [Table 4](#).

A pre-entry visit will take place within 28 days before randomisation, Visit 1. If the subjects are eligible to enter the study they will come to the clinic 8 days (Day -8, Visit 2) before Visit 3 to switch to the Metformin provided by the centre and to check their fasting glucose level. The Metformin treatment will be maintained until the end of the residential period, Visit 3. A follow-up visit (Visit 4) will take place 7-10 days after Visit 3.

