13.2.3 Pharmacodynamics

For the PD efficacy variables (glucose after 20 min and time to reach 3.5 and 5 mmol/L) confidence intervals (95%) will be presented. A mixed model ANOVA with fixed effects for sequence, period and treatment and a random effect for subject within sequence will be used..

All PD-variables will be presented with individual values and descriptive statistics by treatment (with and without glucagon).

For mean values of the PD-variables by time will be presented graphically together in the same plot for with and without glucagon period.

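### Time to recovery (12.4.2) counts crossings produced by the scheduled glucose infusion and meal as recovery; if control recovery is slow, the secondary treatment difference shrinks and its interval is too narrow

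*Protocol*

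**What the plan says.** Protocol section 12.4.2 defines the two secondary variables as minutes from clamp release "to the time point where two consecutive plasma glucose levels" at or above 3.5 and 5.0 mmol/L respectively have been measured. It does not ask whether glucose is being infused or whether the subject has eaten.

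Section 4.1 fixes what happens after release:

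- The clamp is "released at 180 min, ie, insulin infusion will be stopped".
- One hour later, at 240 min, the clamp is reversed so that low glucose does not persist.
- The first step of that reversal reads: "A glucose infusion will be used as needed to achieve a minimum plasma glucose level of 3.2 mmol/L at 240-270 min".
- Two further steps raise the required minimum: "4.0 mmol/L at 270-300 min and ≥ 5.0 mmol/L after 300 min post dosing with AZD1656".
- Ninety minutes after release, "the subjects will be served a meal with food ad libitum".

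Section 4.1 does use an infusion-free condition. Minute-by-minute monitoring runs at least until "two consecutive plasma glucose values are obtained at or above 5.0 mmol/L without concomitant glucose infusion", and a similar condition governs disconnection of the device. Neither sentence defines the endpoint.

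Section 13.2.3 states: "For the PD efficacy variables (glucose after 20 min and time to reach 3.5 and 5 mmol/L) confidence intervals (95%) will be presented". The model is a mixed-model ANOVA with sequence, period and treatment as fixed effects and subject within sequence as random. It makes no provision for censored times.

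**The concern.** The control condition is meant to show spontaneous counter-regulatory recovery (sections 2.2, 3.1 and 6.2.1). Once the required minimum exceeds a threshold, a subject who has not recovered is brought above it by infusion, and 12.4.2 records that moment as the recovery time. A late control time then reports the safety schedule rather than the subject's physiology.

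The ceiling applies to both treatments but falls mainly on the slower one, which the research hypothesis expects to be control. Two consequences would follow for the difference in unassisted recovery time: the estimate moves toward zero, and the capped times bunch together, so the 95% interval is too narrow for that target.

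**Working it through.** **Timeline** (section 4.1; release at 180 min after dosing)

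| Event | Min after dose | Min after release |
|---|---|---|
| Primary glucose reading | 200 | 20 |
| Reversed clamp, minimum 3.2 mmol/L | 240 | 240 − 180 = 60 |
| Minimum 4.0 mmol/L; meal | 270 | 270 − 180 = 90 |
| Minimum 5.0 mmol/L | 300 | 300 − 180 = 120 |

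The 3.2 minimum is below both thresholds and does not itself produce a crossing. The 4.0 minimum exceeds 3.5, so the ceiling for that threshold is about 90 min. The 5.0 minimum meets the other threshold, so its ceiling is about 120 min. Both are soft: a lag can add minutes, and infusion or food can produce a crossing of 5.0 before 120 min.

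**Size of the bias in the mean.** The protocol gives no recovery times, so all inputs here are assumptions. Take a lognormal time T with mean m and standard deviation s, recorded as min(T, c), where c is the ceiling:

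- σ² = ln(1 + s²/m²), μ = ln m − σ²/2, d = (ln c − μ)/σ
- share capped = 1 − Φ(d)
- recorded mean = m·Φ(d − σ) + c·[1 − Φ(d)]

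Example with m = 120, s = 40, c = 120: σ = 0.325, d = 0.162, share capped 0.436. The recorded mean is 120 × 0.436 + 120 × 0.436 = 104.5. Subtracting the glucagon mean of 30 (SD 10, effectively uncapped) gives 74.5 min, against a true 120 − 30 = 90.

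| Threshold (ceiling) | Control mean (SD) | Glucagon mean (SD) | True difference | Recorded difference | Control times capped |
|---|---|---|---|---|---|
| 5.0 (120 min) | 60 (20) | 30 (10) | 30 | 29.8 | 1% |
| 5.0 (120 min) | 120 (40) | 30 (10) | 90 | 74.5 | 44% |
| 5.0 (120 min) | 180 (60) | 30 (10) | 150 | 88 | 86% |
| 3.5 (90 min) | 60 (24) | 15 (5) | 45 | 42.9 | 11% |
| 3.5 (90 min) | 100 (40) | 15 (5) | 85 | 65 | 53% |

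In the third row the recorded control SD falls from 60 to 8 min.

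**Effect on the interval.** A 2×2 crossover with 8 subjects was simulated 40,000 times per case, with a period-adjusted difference and a t interval on 6 degrees of freedom. Assumptions: lognormal times, log-SD 0.4, within-subject correlation 0.3, glucagon median 10 min (to 3.5) or 20 min (to 5.0). Coverage refers to the true difference in unassisted time.

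| Threshold | Control median | Difference, unassisted → recorded | Mean interval width | Coverage |
|---|---|---|---|---|
| 3.5 | 60 | 54 → 51 | 42 → 32 | 93% → 92.5% |
| 3.5 | 90 | 87 → 68 | 64 → 25 | 93% → 3% |
| 5.0 | 60 | 43 → 42 | 42 → 39 | 93.5% → 93% |
| 5.0 | 90 | 76 → 68 | 63 → 41 | 93% → 89% |
| 5.0 | 120 | 108 → 83 | 85 → 34 | 93% → 5% |

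With a control median of 30 min there is practically no effect at either threshold. When half the control times pass the ceiling, the difference falls by 22–23% and the interval narrows by about 60%.

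**The case against.** The strongest reply is that this concerns secondary variables in a small Phase I study, that nothing shows controls recover slowly, and that an analysis plan promised before clean file could set the infusion rule. Individual values will be reported and glucose is followed by the minute, so assisted crossings could be re-derived. Any bias also runs against the research hypothesis.

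Most of this limits the weight of the point without removing it. The size is unknown, and with fast recovery it is negligible. But the definition, the required minimums, the meal and the model are all fixed in the protocol, so a stated rule gives the wrong result rather than a detail being left open. The reversed clamp exists to prevent prolonged hypoglycaemia, so slow recovery is foreseen.

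A second reply is that the capped time is simply a restricted mean. For that target the simulated intervals cover about 87–95%. However, the protocol states no such target or horizon, and assistance starts at 60 min, before either ceiling.

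A reader might infer more than the text supports:

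- That the primary variable is contaminated by the rescue schedule. Its reading at 200 min after dosing comes 40 min before the reversed clamp and 70 min before the meal.
- That the 2.7 mmol/L minimum before 240 min, implied by a footnote to Table 2, forces recoveries. It lies below both thresholds and cannot.
- That the glucagon effect is certainly understated. That requires control times beyond the ceilings.

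**Conclusion.** Wrong as written, for the secondary endpoint; it should be fixed. The mechanism follows directly from sections 4.1, 12.4.2 and 13.2.3: a subject not yet recovered is recorded as recovered by about 90 min (3.5 mmol/L) or 120 min (5.0 mmol/L) because of the schedule, and the ANOVA treats that time as observed spontaneous recovery.

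The consequence is conditional. Under the assumed distributions for 5.0 mmol/L, the loss runs from 0.2 of 30 min (control mean 60) through about 15 of 90 min (mean 120) to 62 of 150 min (mean 180). Interval coverage for unassisted recovery collapses only when about half or more of the control times pass the ceiling. If controls recover within about 60 min, the effect is negligible.

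**What to change.** Leave the clamp, infusion and meal as they are, and change wording only.

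- **Section 12.4.2:** define recovery as two consecutive values at or above the threshold, without concomitant glucose infusion and before the meal. Treat times as right-censored at the first glucose infusion or the meal, whichever comes first.
- **Section 13.2.3:** for these two variables, replace the ANOVA with a paired or crossover method for censored data, and report the number recovered unaided by 60 min per treatment.
- **Any restricted mean:** label it as such and state its horizon; do not present it as the difference in time to recovery.

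Assigning 60 min to everyone not recovered and keeping the ANOVA is a tempting shortcut. It excludes assisted recoveries but tightens the cap: in the case with control mean 180 min, the true 150 min becomes 30 min, with 99.9% of control times capped and a control SD of 0.2 min.

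**Cost:** the device controls the infusion and follows glucose by the minute, so the information should be to hand. If many control periods are censored, the mean difference in minutes may not be estimable, and a rank test alone does not supply the 95% interval that 13.2.3 promises. Infusion is triggered by low glucose, so censoring is related to slow recovery. The count recovered unaided by 60 min should therefore be read alongside the censored analysis.

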Type 1 and 2 diabetic patients with severe hypoglycemia are treated with glucose injections or intra muscular injections with the pancreas hormone glucagon. The latter treatment is crucial for out of hospital events and is often used by bystanders (relatives) as the first treatment when the patient is unconscious. Glucagon acts quickly on the liver and converts stored glycogen into glucose which subsequently is released into the bloodstream. A GKA may interfere with this process due to its effect on liver by increasing available glucose 6-phosphate and thereby the substrate for glycogen production.

Preliminary data from the global SAD (D1020C00001) and MAD (D1020C00002) studies have demonstrated that AZD1656 is rapidly absorbed and maximum concentration (C_{max}) is reached within 1 hour. The compound is rapidly eliminated with a half-life ($t_{1/2}$) of approximately 3-4 hours. AZD1656 is metabolised to the active metabolite AZD12555623. The mean exposure to the metabolite is approximately 20% compared to AZD1656. The C_{max} of the metabolite is reached at the same time as for the parent compound. The initial AZD12555623 decline is parallel to AZD1656 decline but a slower terminal elimination phase is evident. In rats, the exposure to the active metabolite AZD12555623 is approximately 2 fold higher compared to the exposure to AZD1656.

AZ intends to perform genetic research in the AZD1656 clinical development programme to explore how genetic variations may affect the clinical parameters associated with AZD1656.

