4.2 Rationale for study design, doses and control groups

The study will be carried out in subjects with T2DM to allow for results applicable in the target population ie, subjects with T2DM failing on the first line of treatment, Metformin. Before proceeding into larger studies, the availability and security of effective treatment for severe hypoglycaemia are important to define. The CR response, safety aspects and recovery after hypoglycaemia are being assessed in healthy volunteers with unaffected insulin secretion (ie, highly responsive to GK stimulation). The current study will provide important complementary information on these aspects in T2DM patients as well as a comparison between spontaneous recovery from hypoglycaemia with recovery induced by administration of the pancreatic hormone glucagon.

Each subject with T2DM will receive AZD1656 at maximal tolerated dose on top of their normal dose of Metformin. In both hypoglycaemic clamp periods, giving the total daily dose of AZD 1656 and the normal morning dose of Metformin, will induce hypoglycaemia after an overnight fast. For safety reasons as well as to guarantee comparable degrees of hypoglycaemia in both study groups, a hypoglycaemic clamp method will be applied where glucose and insulin will be infused as required in response to a continuous plasma glucose measurement by an automated device, the Biostator[®]. Thereby, plasma glucose levels will be decreased in a step-wise controlled fashion and severe hypoglycaemia with plasma glucose 2.7 mmol/L will not be allowed.

The study subjects will be randomised to receive either an intramuscular dose of glucagon or to participate in a control arm where the recovery from hypoglycaemia is dependent on the CR response. Subjects will then crossover to the reverse treatment in the second hypoglycaemic period after a two days recovery period when the same dose of AZD1656 will be given as during Day 3 and 4 to ensure similar physiological conditions both treatment periods.

A follow-up visit will be conducted within 7 to 10 days after the last dose to assure that all study subjects have a stable glycaemic control and are otherwise healthy leaving the study.

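### Time to recovery counts glucose values reached on the protocol's own glucose infusion and meal, so slow, mainly control, periods are recorded as recovered by about 90 min (3.5 mmol/L) and 120 min (5.0 mmol/L)

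*Protocol*

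**What the plan says.** Protocol Section 12.4.2 defines two secondary variables, each running from release of the clamp (180 min post dose, Section 4.1) "to the time point where two consecutive plasma glucose levels ≥ 3.5 mmol/L and ≥ 5.0 mmol/L respectively, have been measured". The definition says nothing about infused glucose or food.

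Section 4.1 schedules both in every period. From 240 min, "A glucose infusion will be used as needed to achieve a minimum plasma glucose level of 3.2 mmol/L at 240-270 min", followed by "4.0 mmol/L at 270-300 min and ≥ 5.0 mmol/L after 300 min post dosing with AZD1656". Footnotes to Table 2 repeat these levels. Ninety minutes after release, at 270 min post dose, "the subjects will be served a meal with food ad libitum".

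Section 4.1 contains one infusion-free condition. It keeps the Biostator following glucose "at least until two consecutive plasma glucose values are obtained at or above 5.0 mmol/L without concomitant glucose infusion", and a similar condition governs when the device is disconnected.

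Section 4.2 describes the comparator as a "control arm where the recovery from hypoglycaemia is dependent on the CR response". For the three PD efficacy variables, Section 13.2.3 states: "glucose after 20 min and time to reach 3.5 and 5 mmol/L) confidence intervals (95%) will be presented". The model is a mixed model ANOVA with sequence, period, treatment and subject within sequence. Censoring is not mentioned.

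**The concern.** The primary objective (Section 3.1) compares glucagon with spontaneous recovery and names time to recovery as the secondary measure of that comparison. A threshold crossed on infused glucose or after a meal is not spontaneous recovery, yet the definition scores it as such. However slow counter-regulation is under AZD1656, the recorded time cannot go much beyond the point at which the protocol itself lifts glucose over the threshold.

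Three results are at stake: the estimated difference in both times, the width of its CI (values piled up at a ceiling have little spread), and the description of how fast patients recover unaided. Section 2.1 adds a further reason for care, since it notes about glucagon's action that "A GKA may interfere with this process due to its effect on liver". A glucagon period with a poor response would be recorded as recovered at the same ceiling.

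**Working it through.** **Inputs from the protocol.** Release is at 180 min from 2.7 mmol/L. The minimum levels are 3.2 from 240 min, 4.0 from 270 min and 5.0 after 300 min. The meal is at 270 min. The thresholds are 3.5 and 5.0. The protocol states no figure for the ceiling or for unaided recovery, so there is none to reproduce.

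**Step 1: the ceilings.** Minutes after release = minutes post dose − 180.
- Minimum 3.2: 240 − 180 = 60 min (below both thresholds).
- Minimum 4.0: 270 − 180 = 90 min, the first minimum above 3.5.
- Minimum 5.0: 300 − 180 = 120 min, the first minimum at 5.0.
- Meal: 270 − 180 = 90 min.

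With minute-by-minute readings and two consecutive values, the latest recorded times are about 91 and 121 min. These are approximate because the minima are infusion targets. If only the Table 2 sampling times were used, the second qualifying value would fall at 300 − 180 = 120 min and 360 − 180 = 180 min.

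**Step 2: which periods are affected (assumption: linear unaided rise from 2.7).**
- 3.5 is set by the infusion if the rise is below (3.5 − 2.7)/90 × 60 = 0.53 mmol/L per h.
- 5.0 is set by the infusion if the rise is below (5.0 − 2.7)/120 × 60 = 1.15 mmol/L per h.
- The meal can affect 5.0 if the rise is below (5.0 − 2.7)/90 × 60 = 1.53 mmol/L per h.

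| Assumed rise (mmol/L per h) | Unaided 3.5 / 5.0 (min) | Recorded 3.5 / 5.0 (min) |
|---|---|---|
| 0.5 | 96 / 276 | 91 / 121 |
| 0.75 | 64 / 184 | 65 / 121 |
| 1.0 | 48 / 138 | 49 / 121 |
| 1.5 | 32 / 92 | 33 / 93 |

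The recorded time includes the second of two consecutive minute readings. The effect of the meal is not modelled.

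**Step 3: effect on the planned comparison (all means and SDs assumed).** Simulation of 100,000 AB/BA trials with 4 subjects per sequence, a t interval with 6 df, lognormal times and no period effect. For time to 5.0: glucagon mean 20 min, SD 6; control SD 30-45; ceiling 120-130 min. Coverage is the share of 95% intervals that contain the unaided difference.

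| Control mean, unaided (min) | Controls at ceiling, of 8 | Difference understated by (min) | Coverage with ceiling | Coverage without |
|---|---|---|---|---|
| 60 | 0.2-0.7 | 1-4 | 0.90-0.93 | 0.90-0.93 |
| 90 | 0.8-1.6 | 2-8 | 0.91-0.94 | 0.92-0.94 |
| 120 | 2.6-3.6 | 8-17 | 0.59-0.89 | 0.94 |
| 150 | 5.1-6.8 | 24-35 | 0 | 0.94-0.95 |
| 180 | 7.1-7.9 | 50-61 | 0 | 0.94-0.95 |

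Example: with control mean 150, SD 45 and ceiling 120, the unaided difference is 150 − 20 = 130 min with an average CI half-width of 37. The recorded difference is 95 min with a half-width of 10.

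Time to 3.5 behaves the same way (glucagon mean 8, SD 3; control SD 20-35; ceiling 90-100). The understatement is 0-5 min at control means of 45-60, 4-13 min at 90 and 21-32 min at 120.

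**The case against.** The strongest reply is that the protocol already has infusion-free recovery in mind. The monitoring rule in Section 4.1 uses the same two-consecutive-values event at 5.0 without concomitant infusion, so the data will exist. Section 13.1 limits PD analysis to evaluable, appropriate data, and Section 13.3 promises a SAP before clean file. This stands only in part. The rule decides how long glucose is followed and does not define the variable. It does not cover 3.5 or the meal. The reversed clamp and the meal are scheduled procedures, so the exclusion for major deviations does not reach them. Section 12.4.2 is a stated definition, and a SAP that follows it reproduces the problem.

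A second reply stands fully: the size is not shown. The protocol gives no recovery rates, so how many controls would reach the ceiling cannot be derived from it. A reader might infer from the lower rows of the table that the planned intervals will fail. The documents do not support that, because those rows need control means of 150 min or more.

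Third, a reader might infer that the ANOVA must be replaced by one on time restricted to 60 min, which is known in every period if any period given earlier safety glucose is set to 60. That is too strong. With the same assumed inputs and a control mean of 90 min, 6-7 of 8 controls would sit at 60, and the restricted difference is 36-39 min against an unaided 70. It would also discard valid fasting data from 60 to 90 min in subjects who need no glucose. It is a legitimate but different quantity.

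Finally, individual values and mean plots (Section 13.2.3) would make clustering near the ceilings visible, and a poor glucagon response would also show in the 20-minute glucose. Both soften the harm. Neither corrects the estimate or its interval.

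**Conclusion.** The concern holds as a fault in the stated definition. As written, Section 12.4.2 scores glucose supplied by the study as recovery and places ceilings of about 90 min (3.5) and 120 min (5.0) on the recorded times. This follows from the protocol's own clock and needs no assumption beyond minute-by-minute readings and infusion that meets its targets.

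The consequence for the estimates is conditional. Under the assumed inputs it is negligible if controls reach 5.0 in about 60-90 min on average and material from about 120 min, where the difference is understated and its interval too narrow.

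A reader might infer that the trial's main conclusion is at risk. It is not. The primary variable is read 20 min after release, before any scheduled glucose or food. The ceiling is the same in both treatments and binds mainly in the slower one, expected to be control, so it shrinks the glucagon advantage and creates no false superiority claim. The point concerns two secondary variables and should be corrected on that footing.

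**What to change.** **Section 12.4.2.** Count a value only if no glucose has been infused since release and the meal has not been served. Otherwise treat the time as right-censored at the start of glucose infusion or at 270 min post dose, whichever comes first.

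**Section 13.2.3.** Report by treatment the number reaching 3.5 and 5.0 mmol/L unaided by 60 and by 90 min after release, and the number censored. State that censored times are not entered in the ANOVA as observed recoveries. Leave the censored-data method to the SAP; time restricted to 60 min is one option. The SAP should allow for the fact that glucose is started because the level is low, so censoring is related to slow recovery.

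Keep the reversed clamp and the meal unchanged.

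**Cost.** A few sentences of protocol text, and the start time of any infusion taken from the Biostator already in use. Procedures, safety limits and sample size do not change. The downside is that some times become censored, so a mean time to recovery may not be estimable if many controls need glucose.
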